2.3. Sample Size and Power Considerations

The primary efficacy variable for this study is the frequency of CAEs per patient during the 52-week treatment period. The study will be considered positive if the primary efficacy measure indicates a statistically significant treatment effect of reslizumab versus placebo at the respective predefined significance level.

Power calculations were based on the below assumptions:

- Negative binomial (NB) distribution for the number of exacerbations with a mean of 2.9 exacerbations per patient per year for the placebo group
- Dispersion parameter of 1.2
- Treatment effect of 45% between the reslizumab group and the placebo group
- Alpha level of 0.05

Based on the assumptions above, 225 patients per group (450 total) will provide >90% power to detect significant treatment effect of reslizumab over placebo in the reduction of exacerbation rate. The sample size was increased beyond the sample size required to provide 90% power in order to allow sufficient number of patients to assess safety and immunogenicity and to ensure adequate enrollment in the adolescent subset. The current sample size also provides higher power for other efficacy endpoints.

Patients with blood eosinophil levels of 300/ μ L to <400/ μ L will be limited to no more than 30% of patients (60 patients per treatment group).

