4.3. Multiple Comparisons and Multiplicity

A fixed sequence multiple testing procedure will be implemented to test the primary and secondary variables while controlling the overall type I error rate at 0.05. If the resulting two-sided p-value from the primary comparison is ≤ 0.05 , then the next comparison of interest (first secondary variable) will be interpreted inferentially at 0.05. This process continues through the secondary variables until either all comparisons of interest are interpreted inferentially, or until the point at which the resulting two-sided p-value for a comparison of interest is > 0.05 . At the

point where $p > 0.05$, no further comparisons will be interpreted inferentially. The hierarchy of endpoints is as defined in Section 6.3.1.

No multiplicity adjustments will be made for other efficacy and exploratory analyses.

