APPENDIX A. IMPUTATION AND ANALYSIS STEPS FOR ANALYSIS OF THE FREQUENCY OF ASTHMA EXACERBATION

The following represents an outline of the planned methodology for the multiple imputation procedure for the primary analysis of the CAE variable. Minor deviations from this outline can be addressed in the discussion of the results in the CSR. In the situation that more significant updates are warranted, changes will be addressed in a SAP amendment to be finalized prior to database lock.

Step 1: Seed generation.

The seed generation utilized the code below, resulting in a seed (40880) that will be used in the analysis after unblinding.

```
data derived.seed;
  seed = int(time());
  put seed=;
  call symput('seed', left(seed));
run;
```

Step 2: Classify patients with missing data.

Patients in this study will be partitioned into the following 3 categories:

1. ET0; patients who completed all 52 weeks of treatment
2. ET1; patients who withdrew early from treatment but remained in the study contributing post-treatment follow-up data through Week 52
3. ET2; patients who withdrew early from treatment but elected not to remain in the study through Week 52

Step 3: Imputation of missing data.

Using the dataset of ET1 patients for each treatment group, fit a negative binomial regression model to the period of time after treatment withdrawal and estimate the mean number of exacerbations and dispersion parameter k . Let λ denote the estimated rate parameter for one month of duration. For each patient with missing data, derive the duration of missing exposure (T_M) for that patient calculated in months.

Let λ_M denote the unknown rate of exacerbations during the missing exposure period. The exacerbation rate λ_M will be simulated using a Gamma distribution with parameters $\alpha=1/k$ and $\beta=\lambda*k$. Then, the number of events during the missing exposure period will be imputed using a negative binomial distribution with mean λ_M*T_M and dispersion k . For each patient in ET2, sum the observed number of exacerbations during the treatment period with the simulated number during the missing exposure period to obtain the imputed number of exacerbations. This process will be repeated 10 times.

After each iteration, the output dataset of imputed values for ET2 from Step 3 will be appended to the existing data from ET0 and ET1 (from Step 2) to generate 10 complete datasets.

Step 4: Re-run the primary analysis model.

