The negative binomial model will be fitted to the complete set of data for each of the 10 datasets using the same covariates that were used for the primary analysis. The model will include

log(follow-up time) as an offset variable, either excluding/including the summed duration of exacerbations, depending on the analysis. For patients with imputed number of exacerbations, complete follow up of 1 year is assumed. The summed duration of exacerbations will be calculated as summed duration of any exacerbations observed prior to treatment withdrawal + 8 days for each additional (imputed) exacerbation. The assumption of 8 days for the duration of exacerbations is consistent with the minimal duration of exacerbation as derived previously in the BREATH IV program.

Step 5: Multiple imputation and associated combining rules applied to propagate imputation uncertainty (Little and Rubin 2002).

The output datasets from Step 4 will contain inferential statistics for each imputation iteration. The SAS[®] procedure PROC MIANALYZE will be used to generate an overall p-value and 95% CI for the treatment difference; results will be exponentiated back to their original scale.

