APPENDIX B. TIPPING POINT ANALYSIS

The tipping point analysis evaluates several combinations of imputed missing data values until the analysis reaches a “tipping point” or point at which a particular combination of imputed missing data changes the study conclusions, as summarized by its p-value. This is a sensitivity analysis utilizing multiple imputations under the missing not at random (MNAR) assumption, and will only be conducted if a significant result ($p \leq 0.05$) is observed as part of the primary analysis. If the sensitivity analysis reveals that the tipping point consists of unreasonable values, then the robustness of the study results is supported. This is in accordance with the recommendation discussed in the "Prevention and Treatment of Missing Data in Clinical Trials Report" ([National Research Council 2010](#)).

The following represents an outline of the planned methodology for the “tipping point” multiple imputation sensitivity analysis of the CAE variable. Minor deviations from this outline can be addressed in the discussion of the results in the CSR. In the situation that more significant updates are warranted, changes will be addressed in a SAP amendment to be finalized prior to database lock.

Exacerbations will be imputed for patients who discontinued treatment prior to the endpoint of the study. Multiple imputation and associated combining rules will be applied to propagate imputation uncertainty (see [Appendix A](#) for additional details). In the following analysis, the number of exacerbations in the control group will be imputed assuming that missing data are MAR. For the treatment group, the number of exacerbations will be multiplied by a constant scale factor (>1) to allow for MNAR. In the treatment group, this scale will be progressively increased and the process repeated until the treatment effect is no longer significant at the 5% level. The value of the scale parameter at which the treatment effect is no longer significant is called the “tipping point”.

The tipping point analysis will be performed according to the following steps.

1. Values will be imputed assuming MAR in both treatment groups using the multiple imputation procedures described in [Appendix A](#) (Steps 1-3). This process will be repeated 10 times.

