2. To allow for MNAR in the reslizumab treatment group, a scale parameter will be used to adjust imputed values for the number of CAEs, by multiplying the imputed values by the scale parameter. The following pseudo-code can be used to demonstrate this concept, where OUTMI is the output dataset(s) from the Step 1, COMPLETER identifies the patients who discontinued treatment early with incomplete follow-up, NUMCAE is the number of exacerbations, and λ is the scale parameter.

```
data outmi;
  set outmi;
  if armcd='RESLIZUMAB' and COMPLETER='N' then numcae=numcae* $\lambda$ ;
run;
```

After this step, 10 datasets with complete data have been created.

3. The negative binomial model will be fitted to the complete set of data for each of the 10 datasets using the same covariates that were used for the primary analysis, following the same outline described in [Appendix A](#) (Step 4).

4. Apply combining rules to the results from the 10 datasets using PROC MIANALYZE, as described in [Appendix A](#) (Step 5).
5. Repeat Steps 1-4 (above) using escalating values for the scale parameter (eg, 1, 2, 3, 4, etc.) resulting in estimates of the CAE rate ratio and p-values for each scale parameter.

The rate ratio of CAEs and associated p-value will be summarized corresponding to each selected scale value (eg, 1, 2, 3, 4, etc.) until the tipping point is achieved.

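### Ten imputations leave avoidable Monte Carlo noise in the pooled primary p-value and, more durably, in the tipping point

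*SAP*

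**What the plan says.** SAP Appendix A, Step 3 imputes post-withdrawal exacerbation counts for group ET2, the patients who stopped treatment and left the study before Week 52. It then states: "This process will be repeated 10 times". Step 4 fits the negative binomial model to each completed data set. In Step 5, "PROC MIANALYZE will be used to generate an overall p-value and 95% CI for the treatment difference".

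Step 1 fixes the random seed in advance, "resulting in a seed (40880) that will be used in the analysis after unblinding".

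Appendix B, Step 1 imputes both arms "using the multiple imputation procedures described in" Appendix A, again ten times. The reslizumab imputed counts are then multiplied by a scale factor; "this scale will be progressively increased and the process repeated until the treatment effect is no longer significant at the 5% level". The example grid is the integers 1, 2, 3, 4 and so on. This analysis runs only if the primary result is significant.

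Neither document justifies ten imputations, sets a limit on Monte Carlo error, or gives an expected size for ET2.

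**The concern.** A pooled estimate from m imputations is itself a random draw, and its spread over seeds shrinks only as m grows. Ten is a small number for a p-value compared with a sharp threshold. Under SAP section 4.3 the primary p-value opens the fixed sequence: if it exceeds 0.05, none of the nine ordered secondary endpoints in section 6.3.1 can be interpreted inferentially. Appendix B is also skipped in that case.

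The tipping point has its own exposure. It is defined as the scale at which p crosses 0.05, so it is always read where the noise matters, however clear the primary result was.

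**Working it through.** **Inputs from the documents.** Placebo rate 2.9 per patient-year, negative binomial, dispersion 1.2, 45% reduction, 225 per group, "Alpha level of 0.05" (SAP section 2.3); two-sided test (section 4.3); m = 10 and seed 40880 (Appendices A and B).

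**Input not in the documents.** The share of patients imputed. I take 2% to 15% as an assumed range.

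**1. The plan's own power figure.** The reslizumab rate is 2.9 × 0.55 = 1.595. Var(log rate ratio) = [(1/2.9 + 1.2) + (1/1.595 + 1.2)]/225 = 0.01499, so SE = 0.1224. Expected z = −ln(0.55)/0.1224 = 0.598/0.1224 = 4.88. Power = Φ(4.88 − 1.96) = 99.8%. This reproduces the figure above 99% in the protocol synopsis and satisfies the figure above 90% in SAP section 2.3.

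**2. Size of the seed noise.** The SD of the pooled z over seeds is about √(FMI/m), where FMI is the between-imputation share of the total variance. For FMI = 10%, √(0.10/10) = 0.10 and √(0.10/100) = 0.03. Going from 10 to 100 divides the noise by √10, about 3.2.

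Simulating Step 3 as written (a gamma draw of the rate, then a negative binomial count), with m = 10:

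| Assumed share imputed | SD of pooled z |
|---|---|
| 2% | 0.04 |
| 5% | 0.07 |
| 10% | 0.10 |
| 15% | 0.10 |

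With m = 100 the SD is 0.01–0.03. A separate simulation at 8% and 15% imputed gave 0.09–0.12 (m = 10) and 0.03–0.04 (m = 100). The combined range is 0.04–0.12 against 0.01–0.04.

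**3. Translation to p.** If unlimited imputations would give z = 1.96, the 95% range of z over seeds is 1.96 ± 1.96 × SD.

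| SD | z range | p range |
|---|---|---|
| 0.01 | 1.940–1.980 | 0.048–0.052 |
| 0.04 | 1.882–2.038 | 0.042–0.060 |
| 0.09 | 1.784–2.136 | 0.033–0.075 |
| 0.12 | 1.725–2.195 | 0.028–0.085 |

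Single simulated trials with p near 0.05 agree. They used a true rate ratio of 0.79, no covariates, a one-year offset, and a post-withdrawal rate equal to the arm's rate. The first column gives the p-value from a large number of imputations.

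| Share imputed; p | m = 10: 95% range; seeds above 0.05 | m = 100: 95% range; seeds above 0.05 |
|---|---|---|
| 2%; 0.048 (plain negative binomial draw) | 0.042–0.056; 30% | 0.046–0.051; 6% |
| 5%; 0.044 (Step 3 as written) | 0.033–0.061; 22% | 0.040–0.049; 1% |
| 10%; 0.046 (Step 3 as written) | 0.030–0.074; 34% | 0.040–0.053; 10% |

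**4. How likely a borderline primary result is.** At expected z = 4.88, the chance that z falls between 1.725 and 2.195 (the widest zone above) is Φ(−2.685) − Φ(−3.155) = about 0.3%. With a weaker true rate ratio of 0.65, the reslizumab rate is 1.885, SE = √{[(1/2.9 + 1.2) + (1/1.885 + 1.2)]/225} = 0.1207 and expected z = 0.431/0.1207 = 3.57. The chance is then about 5%.

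**5. Tipping point.** Three simulated trials on the integer grid, with plain negative binomial draws and fresh imputations at each scale:

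| Share imputed; starting p | m = 10 | m = 100 |
|---|---|---|
| 10%; 0.001 | scale 3: 42%, 4: 58% | 3: 15%, 4: 85% |
| 10%; 0.012 | 3: 72%, 4: 27% | 3: 96%, 4: 4% |
| 5%; 0.012 | 3: 40%, 4: 57%, 5: 3% | 3: 21%, 4: 79% |

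Multiplying imputed counts by the scale factor also raises the between-imputation variance. In a simulation with 8% imputed and an assumed rate ratio of 0.68, FMI rose from 0.06 at scale 1 to 0.45 at scale 6. The SD of the pooled z rose from 0.08 to 0.21 with m = 10; with m = 100 it was 0.07 at scale 6.

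**The case against.** A reader might infer that the primary p-value can be steered by the choice of seed, or that ten imputations make the test invalid. The documents support neither. Seed 40880 is written into the SAP, so one number will be reported and anyone can reproduce it. Rubin's rules, applied through PROC MIANALYZE, add the (1 + 1/m) between-imputation term and adjust the degrees of freedom, so finite m is already carried into the standard error. No bias or Type I error inflation has been shown.

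The imputed share may also be small. Protocol sections 4.4.1 and 4.4.2 ask patients to keep attending visits after stopping treatment, and ask sites to seek exacerbation status at Week 52 even when contact is lost. At 2% imputed, only p-values within roughly 0.01 of 0.05 are affected.

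The tipping point belongs to a sensitivity analysis, is judged on whether the scale is plausible, and has a coarse grid. Appendix B can also be read as reusing the same seeded draws at every scale, in which case noise is shared across scales and the frequencies above would differ. The location of the crossing would still depend on the one set of draws.

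All of this stands and limits the weight of the point. It does not supply a reason for ten: a fixed seed prevents selection but does not make a single noisy draw precise.

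**Conclusion.** The point holds as a minor, nearly free improvement in precision. With 2% to 15% of patients imputed (an assumption), ten imputations leave an SD of about 0.04 to 0.12 in the pooled z, against about 0.01 to 0.04 with 100. The upper p range, 0.028–0.085, rests on the largest SD found and should not be read as typical.

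For the primary test the practical risk is small if the design assumptions are right, and larger if the true effect is weaker. The tipping point is the more durable exposure, with a shift of about one integer step in the examples. One hundred imputations reduce the noise but do not abolish it: in the example with p = 0.046 and 10% imputed, 10% of seeds still exceeded 0.05.

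**What to change.** Keep seed 40880. Raise the number of imputations to at least 100 in Appendix A, Step 3 and Appendix B, Step 1, and report the Monte Carlo error of the pooled p-value beside the primary result. Make the change by SAP amendment before database lock. Appendix A lets minor deviations be described in the CSR, but a change to the procedure that produces the primary p-value is better settled before unblinding. The cost is a short amendment and minutes of computing time; design, data and estimand are unchanged.

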APPENDIX B. TIPPING POINT ANALYSIS

The tipping point analysis evaluates several combinations of imputed missing data values until the analysis reaches a “tipping point” or point at which a particular combination of imputed missing data changes the study conclusions, as summarized by its p-value. This is a sensitivity analysis utilizing multiple imputations under the missing not at random (MNAR) assumption, and will only be conducted if a significant result ($p \leq 0.05$) is observed as part of the primary analysis. If the sensitivity analysis reveals that the tipping point consists of unreasonable values, then the robustness of the study results is supported. This is in accordance with the recommendation discussed in the "Prevention and Treatment of Missing Data in Clinical Trials Report" ([National Research Council 2010](#)).

The following represents an outline of the planned methodology for the “tipping point” multiple imputation sensitivity analysis of the CAE variable. Minor deviations from this outline can be addressed in the discussion of the results in the CSR. In the situation that more significant updates are warranted, changes will be addressed in a SAP amendment to be finalized prior to database lock.

Exacerbations will be imputed for patients who discontinued treatment prior to the endpoint of the study. Multiple imputation and associated combining rules will be applied to propagate imputation uncertainty (see [Appendix A](#) for additional details). In the following analysis, the number of exacerbations in the control group will be imputed assuming that missing data are MAR. For the treatment group, the number of exacerbations will be multiplied by a constant scale factor (>1) to allow for MNAR. In the treatment group, this scale will be progressively increased and the process repeated until the treatment effect is no longer significant at the 5% level. The value of the scale parameter at which the treatment effect is no longer significant is called the “tipping point”.

The tipping point analysis will be performed according to the following steps.

1. Values will be imputed assuming MAR in both treatment groups using the multiple imputation procedures described in [Appendix A](#) (Steps 1-3). This process will be repeated 10 times.
2. To allow for MNAR in the reslizumab treatment group, a scale parameter will be used to adjust imputed values for the number of CAEs, by multiplying the imputed values by the scale parameter. The following pseudo-code can be used to demonstrate this concept, where OUTMI is the output dataset(s) from the Step 1, COMPLETER identifies the patients who discontinued treatment early with incomplete follow-up, NUMCAE is the number of exacerbations, and λ is the scale parameter.

```
data outmi;
  set outmi;
  if armcd='RESLIZUMAB' and COMPLETER='N' then numcae=numcae* $\lambda$ ;
run;
```

After this step, 10 datasets with complete data have been created.

3. The negative binomial model will be fitted to the complete set of data for each of the 10 datasets using the same covariates that were used for the primary analysis, following the same outline described in [Appendix A](#) (Step 4).

4. Apply combining rules to the results from the 10 datasets using PROC MIANALYZE, as described in [Appendix A](#) (Step 5).
5. Repeat Steps 1-4 (above) using escalating values for the scale parameter (eg, 1, 2, 3, 4, etc.) resulting in estimates of the CAE rate ratio and p-values for each scale parameter.

The rate ratio of CAEs and associated p-value will be summarized corresponding to each selected scale value (eg, 1, 2, 3, 4, etc.) until the tipping point is achieved.

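### SAP Appendices A and B use *imputed* in two senses, and the tipping-point code, taken literally, scales recorded as well as simulated exacerbations

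*SAP*

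**What the plan says.** Appendix B opens by saying "The tipping point analysis evaluates several combinations of imputed missing data values" until significance is lost. If the scale at that point is implausible, the result is to be taken as robust. The analysis runs only if the primary p-value is at most 0.05.

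Step 1 runs Appendix A Steps 1 to 3. Step 2 relaxes missing at random in the reslizumab arm "by multiplying the imputed values by the scale parameter". It continues: "The following pseudo-code can be used to demonstrate this concept", where "OUTMI is the output dataset(s) from the Step 1" and "NUMCAE is the number of exacerbations". The line is "if armcd='RESLIZUMAB' and COMPLETER='N' then numcae=numcae", multiplied by the scale. COMPLETER='N' marks early discontinuers without full follow-up, the group that Appendix A calls ET2.

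Three other statements bear on what is scaled:
- Appendix A Step 3 sums, for each ET2 patient, "the observed number of exacerbations during the treatment period with the simulated number during the missing exposure period to obtain the imputed number of exacerbations".
- Appendix A Step 4 sets exacerbation time as the observed durations before withdrawal plus "8 days for each additional (imputed) exacerbation".
- The introduction to Appendix B also says, with no limit to simulated events, that the reslizumab exacerbation count is multiplied by a fixed factor above 1.

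**The concern.** *Imputed* means only the added, simulated events in Appendix A Step 4, and the opening of Appendix B ties it to missing data. In Appendix A Step 3 it labels the observed-plus-simulated total. The code multiplies that total, and nothing in either appendix separates the two parts before scaling.

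An assumption about unobserved outcomes gives no reason to alter recorded ones. The output is a single number whose plausibility the reader must judge. A tipping scale of 5 would naturally be read as saying that the missing period needs five times the imputed events to overturn the result. If recorded events were multiplied too, that reading is wrong, and a sound positive result could look more fragile than it is.

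**Working it through.** **Base case.** SAP Section 2.3 gives 225 patients per group, a placebo rate of 2.9 per year, dispersion 1.2 and a 45% reduction. The reslizumab rate is therefore 2.9 × 0.55 = 1.595. The Wald standard error of the log rate ratio is √[((1/2.9 + 1.2) + (1/1.595 + 1.2))/225] = 0.1224. With ln 0.55 = −0.598, power at two-sided 0.05 is 99.8%. This agrees with the >99% in the protocol synopsis and the >90% in the SAP. The documents state no tipping-point value to reproduce.

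**Algebra.** For one reslizumab ET2 patient at scale s:
- missing data only: O + s × S
- code taken literally: s × (O + S)
- excess: (s − 1) × O, never negative, and zero at s = 1 or O = 0

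With O = 2, S = 1 and s = 3, the counts are 5 and 9.

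**First simulation.** It used the inputs above. Assumed, because the documents do not say:
- 5%, 10% or 20% per arm with incomplete follow-up, and the same share withdrawn from treatment but followed
- withdrawal spread from month 1 to week 51, or confined to months 6 to 12
- a post-withdrawal reslizumab rate equal to its own arm's rate or to the placebo rate

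Imputation followed Appendix A Step 3 with 10 datasets and Rubin's rules. The model was negative binomial with treatment only and one year's exposure. There were 100 trials per setting, with integer scales up to 60. Median first non-significant scale, coded rule v simulated events only:

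| Withdrawal, post-withdrawal rate | 5% | 10% | 20% |
|---|---|---|---|
| Spread, own arm | 10 v 16.5 | 5 v 8 | 3 v 5 |
| Spread, placebo | 6 v 8 | 4 v 4 | 2 v 3 |
| Months 6–12, own arm | 10 v 23 | 5 v 13.5 | 4 v 8 |
| Months 6–12, placebo | 7.5 v 13 | 4 v 7 | 3 v 5 |

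Of 591 significant trials with spread withdrawal, the coded rule tipped earlier in 464, at the same integer in 127 (21%) and later in none. Of 599 with late withdrawal, it tipped at the same integer in 20 and later in none. The gap is wider with late withdrawal because more of the count is observed: at the own-arm rate the median observed-to-simulated ratio was about 3.0, against 1.1 when spread.

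The spread settings were repeated with 8 days deducted per unscaled event. The medians were 11.5 v 18.5, 6 v 8 and 4 v 5 (own arm), and 7 v 8, 4 v 4 and 3 v 3 (placebo). Of 551 significant trials, 409 tipped earlier, 142 at the same integer and none later.

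**Second simulation.** This set the imputation rate and dispersion at their true values instead of estimating them from followed withdrawals, with withdrawal spread over the year. At rate ratio 0.55 the medians were 8 v 11, 5 v 7 and 3 v 4. At 0.70 they were 4 v 6, 3 v 3 and 2 v 3. Of 333 significant trials, 249 tipped earlier, 84 at the same integer and none later. A smaller run at 10% incomplete follow-up with the 8-day deduction gave 37 earlier, 31 the same and none later, out of 68.

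**The case against.** The strongest reply is that sentence and code agree under the SAP's own label. Appendix A Step 3 names the summed count the imputed number, and the introduction to Appendix B speaks of multiplying the exacerbation count. This stands in part. A reader might infer that the code is the only scaling rule given, or that it flatly contradicts the sentence it illustrates. Neither is supported: there are two prose rules, one of which fits the code. What remains is one word with two meanings, in an analysis whose declared object is the missing data.

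The code is also only illustrative, and both appendices are outlines from which minor departures may be explained in the study report. A programmer could therefore scale only the simulated events. That leaves room for the right analysis but does not specify it.

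A reader might also infer that the rule could flatter reslizumab. The excess in the algebra is never negative, and no simulated trial tipped later under the coded rule, so the error runs against the sponsor.

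Finally, the medians are not estimates for this trial. The documents give no dropout share, timing or post-withdrawal rate. At 5%, the group of followed withdrawals holds only about 11 patients per arm (0.05 × 225), so those medians are unstable. The second simulation gave smaller gaps at rate ratio 0.55. This stands: the direction is firm and the size is conditional.

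**Conclusion.** The point holds as an inconsistency of terms whose coded resolution is the wrong one for this purpose. Followed literally, the analysis inflates recorded reslizumab events, and its tipping scale cannot be read as a multiplier on the missing period. Robustness is understated or unchanged. With incomplete follow-up of 5% to 20% spread over the year, rate ratio 0.55 and one year's exposure, the first simulation's medians range from no difference (4 v 4) to 10 v 16.5. Those dropout figures are assumptions.

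It should be corrected, but it does not threaten the trial's conclusion. A reader might infer that the primary analysis or error control is compromised. It is not: the two rules coincide at scale 1, the analysis follows only a significant primary result, and it plays no part in the fixed testing sequence of SAP Section 4.3.

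**What to change.** Before database lock, amend Appendices A and B:
- Hold observed and simulated counts as separate variables. The 8-day rule in Appendix A Step 4 already needs this.
- Replace the code line with numcae = observed + scale × simulated for reslizumab ET2 patients.
- Align the multiplication sentence in the introduction to Appendix B.
- Use *imputed* only for simulated missing-period events in both appendices.

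As a secondary clarification, state that the 8-day deduction uses the unscaled simulated count. The documents do not say that it uses the scaled one, so this adds no weight to the main point. If it did, 46 events × 8 days = 368 days would exceed the assumed year and leave the log offset undefined.

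The cost is one line of code and a few words of definition. No data collection changes.
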